9.2.3 Genomic testing

Paraffin embedded tumor tissue sections and one whole blood sample will be collected and processed for a 410 gene panel DNA sequencing analyses. The treatment and preservation of

tumor tissue will follow the routine operation procedures in pathology. Tissue blocks with high levels of tumor cells should be selected (weight 100~500 mg, diameter >5 mm). At least 15-20 unstained and charged slides should be provided, with a thickness of 10 μ m, along with one HE stained paraffin sections with a thickness of 5 μ m. Slides should be cut from the same source. The predicted tumor cells should be more than 50%. The tissue section samples will be shipped to MSKCC after collection for further testing and analysis. The tumor cell DNA will be extracted, sequenced and analyzed based on standard operational procedures at the MSKCC research laboratory. One whole blood sample should be collected in a 3mL EDTA lavender top tube and send to MSKCC. MSKCC's Center of Molecular Oncology will run its Integrated Mutation Profiling of Actionable Cancer Targets (IMPACT) battery of 410 cancer genes on all samples provided. This information will be collected for research purposes only.

9.2.4 Tumor biopsy:

Tumor biopsies will be performed as per local institutional guidelines. Tumor biopsy (optional) baseline up to 30 days prior to initiation of dosing (if patient had a biopsy after any previous treatments, they would be exempt of this biopsy) and at the end of treatment Cycle 2 (or Day 1 of cycle 3) in line with the imaging for tumor measurement. An additional optional biopsy at the time of disease progression will be performed in patients who have complete response, partial response or stable disease for > 16 weeks. If either the baseline or post-treatment biopsy is unable to be obtained due to technical issues (after consenting the patient and making a reasonable effort), the patient is still eligible to participate in the study. A third optional biopsy will take place at the time of disease progression for patients who have complete response, partial response, or stable disease for \geq 16 weeks. Biopsy samples obtained pre- or after treatment will also be used for biomarker analysis using immunohistochemistry methods as described above. For tissue biopsy, multiple strips that are sufficient for biomarker study should be provided.

A 3mL blood sample will be collected at each time the biopsy is performed. The blood will be drawn in an EDTA tube and MSKCC's Center of Molecular Oncology will run the sample on its Integrated Mutation Profiling of Actionable Cancer Targets (IMPACT) battery of 410 cancer genes. The sample may also be used to identify predictive biomarkers of response, sensitivity and clinical benefit to ENMD-2076.

Tumor biopsy for minor patients will only occur if medically indicated and not solely for research purposes. If available, a sample of tumor tissue from any surgical resection or biopsy during treatment or at time of progression will be requested for biomarker and genomic testing on this study. The biopsy after cycle 2 and the optional biopsy at completion of therapy only refers to patients 18 years of age or older.

(A manual for the Pathology tissue and Tumor biopsy will be provided)

10. STATISTICAL METHODS PLANNED AND SAMPLE SIZE

10.1 Subject Populations

All enrolled patients who receive at least one dose of study medication will constitute the safety population. The safety population will be used for all demographic and baseline characteristics analyses and for all safety analyses.

The per-protocol population will include all evaluable patients in the safety population who do not have a major protocol deviation. Efficacy assessments will be analyzed for the safety and per-protocol population. The analysis on the safety population should be considered primary.

10.2 Subject Disposition

This study is an open-label trial; patients will be allowed to continue study drug treatment until disease progression or toxicity occurs. Patients will remain on study for at least 6 months/180 days. No interim analysis or data safety monitoring beyond that described above will be conducted for this study.

10.3 Demographics and Baseline Characteristics

Demographics and baseline characteristics of subjects will be summarized with descriptive statistics.

10.4 Efficacy Analysis

We have designed this study using a Simon's Optimal two-stage design to allow for an early interim analysis to determine potential futility and an overall final analysis with criteria established to allow for sufficient power and type 1 error rate to provide results to support a submission of the study as a pivotal trial.

For the primary endpoint, the overall response rate will be examined using the RECIST v 1.1 criteria. Patients will first be examined in one of 4 categories – CR, PR, SD, PD (Complete response, Partial Response, Stable Disease, or Progressive disease, respectively). Next, patients will be dichotomized as responders (CR/PR versus non-responders). The null hypothesis that the true response rate is 2% will be tested against a one-sided alternative that the true response rate is 15%. In the first stage, 16 patients will have reached study endpoints of response s per RECIST 1.1 criteria after two cycles of treatment. If there are zero responses in these 16 patients, the study will be stopped. Otherwise, 13 additional patients will be accrued for a total of 29. The null hypothesis will be rejected if 2 or more responses are observed in 29 patients. This design yields a type I error rate of 9.4% and power of 90% when the true response rate is 15%. The probability of early termination due to drug inefficacy is 72%.

After the primary efficacy analysis is performed, a one-sided 95% confidence interval will be calculated using the Clopper-Pearson exact method for the response rate. This will determine the

lower bound for the response rate. If 2 or more patients respond out of 29 then the lower bound will exceed 1.2% providing evidence that the drug is active (i.e. ruling out 0% response). For each of the secondary endpoints, exploratory analyses will be performed. Progression Free Survival rate at 6 months (PFS6) and three time-to-event measures will be calculated. Time to Progression, progression free survival and overall survival. A Kaplan-Meier survival plot will be calculated for each of these measures and median time to event (i.e. survival) will be calculated for each measure.

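### The planned Clopper-Pearson lower bound in section 10.4 ignores the two-stage design, so at 2 of 29 it includes the 2% rate that the trial's own test rejects.

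*Combined protocol and SAP*

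**What the plan says.** Section 10.4 of the combined protocol and SAP states: "We have designed this study using a Simon's Optimal two-stage design". The null response rate is 2% and the one-sided alternative is 15%. On the first stage it says: "If there are zero responses in these 16 patients, the study will be stopped". A trial that passes this stage enrols 13 more patients, 29 in all. The final rule reads: "The null hypothesis will be rejected if 2 or more responses are observed in 29 patients". The stated operating characteristics are a type I error of 9.4%, power of 90% and a 72% probability of early termination.

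After the primary analysis, "a one-sided 95% confidence interval will be calculated using the Clopper-Pearson exact method for the response rate". The section says that with 2 or more responses in 29 the lower bound will exceed 1.2%, and it reads this as evidence of activity because a 0% rate is ruled out. It gives no adjustment of the bound for the first-stage stop, and it names no point estimator.

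**The concern.** The test and the interval rest on different sampling distributions. The test counts a trial as a rejection only if it passed stage 1; the bound treats 29 patients as if they had been enrolled in one step. The levels also differ: the test has one-sided error 9.4% and the bound 5%.

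Both differences bear on 2 of 29, the rejection boundary and the only result for which the section gives a bound. A report with that result would state that 2% is rejected and print a lower bound well under 2%. A reader who asks whether 2% is excluded would get two answers from the same data. Section 10.4 also says the results should be able to support a pivotal submission, so the question is likely to be asked.

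**Working it through.** **Inputs**, all from section 10.4: first stage 16, second stage 13, total 29; stop at 0 of 16; reject at 2 or more of 29; null 2%, alternative 15%; one-sided 95% Clopper-Pearson bound, stated to exceed 1.2% at 2 of 29. Write X1 and X2 for the responses in each stage, p for the true rate and q = 1 − p.

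**1. The test is two-stage.** The trial rejects unless X1 = 0, or X1 = 1 and X2 = 0:

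P(reject) = 1 − q^16 − 16·p·q^28

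- p = 0.02: 1 − 0.7238 − 0.1818 = 0.0944 (stated 9.4%)
- p = 0.15: 1 − 0.0743 − 0.0253 = 0.9004 (stated 90%)
- Early termination at 2%: 0.98^16 = 0.7238 (stated 72%)

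A fixed sample of 29 with the same cut-off has P(reject) = 1 − q^29 − 29·p·q^28. That is 1 − 0.5566 − 0.3294 = 0.1140 at 2% and 0.9451 at 15%, which are not the plan's figures.

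**2. The bound is fixed-sample.** The Clopper-Pearson bound at 2 of 29 solves 1 − q^29 − 29·p·q^28 = α. With α = 0.05 this gives p = 1.239%, which is the plan's 1.2%.

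**3. The two-stage bound.** Order outcomes by total responses, with the 0 of 16 stop lowest, and solve P(X1 ≥ 1 and X1 + X2 ≥ x | p) = α. At x = 2 this is 1 − q^16 − 16·p·q^28 = α, the test's own rejection probability.

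Lower bound at 2 of 29:

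| One-sided level | Clopper-Pearson, n = 29 | Exact two-stage |
|---|---|---|
| 95% | 1.24% | 1.38% |
| matched (α = 0.09445, 90.6%) | 1.79% | 2.00% |
| 90% | 1.85% | 2.07% |

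Clopper-Pearson stays below 2% in every row. Its p-value against 2% is 0.114, so it excludes 2% only at about one-sided 88.6% or lower. The two-stage bound at the matched level equals 2.00% by construction. The match needs the unrounded error: with α = 0.094 the two-stage bound is 1.99%.

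**4. Source of the gap.** Changing the level first moves Clopper-Pearson from 1.24% to 1.79% (0.55 points); the stopping adjustment then moves it from 1.79% to 2.00% (0.21 points). Neither is enough alone: the level change stops at 1.79%, and the stopping adjustment at 95% stops at 1.38%.

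**5. Validity of the planned bound.** For any p, the bound exceeds p only if the trial reaches 29 with at least some number of responses. That event lies inside the corresponding fixed-sample event, so the miss rate cannot exceed 5% (taking the bound as 0 after a stop at 0 of 16). Exact enumeration gives coverage of 98.2% at 2% and 97.8% at 15%, with a minimum of 95.04% over rates from 0.25% to 49.75%.

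**6. How often the boundary result arises.** The probability of exactly 2 of 29 after passing stage 1 is (208 + 120)·p²·q^27. At 2% this is 0.0760, about 80% of the 0.0944 rejection probability.

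**7. Point estimate.** If the crude proportion is used, 2 of 29 is 6.9%. The unbiased two-stage estimate (UMVUE) is (13 + 15)/(208 + 120) = 28/328 = 8.5%. Averaged over all trials, including those that stop, the crude rate is biased downward: −0.65 points at 2%, about −1.0 near 6% (the largest) and −0.50 at 15%.

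**The case against.** The strongest reply is that nothing here is an error of inference. The decision rests on the count of responders. The interval comes afterwards, and its stated purpose is to rule out 0%, not 2%; either bound does that. A stop for futility only removes high outcomes, so the fixed-sample bound errs low and cannot overstate activity. At 95% the two methods differ by at most 0.145 points over all totals from 1 to 29. From 3 of 29 upwards both exceed 2% even at 95% (2.880% and 2.965% at 3 of 29). Most of the visible conflict is the choice of 95%.

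All of that stands, and it limits the point. It does not remove the mismatch at 2 of 29: once the level is matched, the fixed-sample bound still includes the rate that the test rejects.

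Three stronger readings are tempting, and the documents do not support them:

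- *The interval is invalid.* Step 5 of the working shows that it keeps at least its nominal coverage. Coverage well above 95% at some rates is mostly discreteness, not the stopping rule: at a true 15% the miss rate is 2.23% both with a fixed 29 and under the two-stage design.
- *The plan claims that the interval excludes 2%.* Section 10.4 makes no such claim.
- *The plan adopts a biased point estimate.* It names no estimator, so this rests on assuming the crude proportion, whose bias is downward and at most about 1 point.

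**Conclusion.** The point holds as an inconsistency in reporting. Section 10.4 tests 2% with the two-stage distribution at 9.4% and bounds the rate with a fixed-sample distribution at 5%. The bound is valid but conservative. At 2 of 29 the test rejects 2%, while the planned bound is 1.24%, and 1.79% at the test's own level; the two-stage bound at that level is 2.00%. The method-specific disagreement is confined to that one outcome, which is also the rejection boundary and the most likely rejecting result under the null.

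The figures assume that the design runs as written (exactly 16 then 13 patients, the stop at 0 of 16 obeyed) and that outcomes are ordered by total responses with the early stop lowest. The estimator figures also assume the crude proportion. Conclusions about the decision rule, sample size, type I error and power are unaffected.

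**What to change.** In section 10.4, replace the fixed-sample Clopper-Pearson bound with the exact two-stage lower bound that solves P(X1 ≥ 1 and X1 + X2 ≥ x | p) = α.

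- Set α to the design's attained one-sided error, held unrounded (0.09445), so that the bound reaches 2% exactly when the test rejects.
- Report the one-sided 95% two-stage bound beside it.
- Restate the 1.2% figure: at 2 of 29 the two-stage bound is 1.38% at 95% and 2.00% at the matched level.
- State that the lower bound is 0 after a stop at 0 of 16.
- Optionally, report the UMVUE or a median-unbiased estimate beside the crude rate (8.5% against 6.9% at 2 of 29).

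The cost is SAP wording and a few lines of code, with no extra patients or data. The downside is a little more analysis work and an interval that readers know less well than Clopper-Pearson.

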10.5 Safety Analysis

Safety will be assessed by evaluation of adverse events and clinical laboratory results.

10.5.1 Adverse Events

Adverse events will be coded to system organ class and preferred term using MedDRA version 16.0 or higher. All adverse events occurring after the initiation of the study treatment (treatment emergent adverse events) will be reported, including events present at baseline that worsened during the study.

Adverse events will be summarized by treatment group to provide visual comparison among the treatment groups with respect to incidence of adverse events (the number of subjects reporting at least one episode of a specific adverse event), incidence of adverse events by severity within body system, incidence of adverse events by attribution within body system, and incidence of adverse events causing withdrawal and incidence of serious adverse events. Regarding severity and attribution summaries, the most extreme outcome (highest severity and closest to study drug related) will be used for those subjects who experience the same adverse event on more than one occasion.

Written narratives will be provided for all serious, unexpected or other significant adverse events that are judged to be of special interest because of their clinical importance.

10.5.2 Clinical Laboratory

Clinical laboratory results will be summarized with descriptive statistics at baseline each study timepoint and with shifts from baseline.

11. QUALITY CONTROL AND QUALITY ASSURANCE

10.6 Source Data and Records

Source data are all the information in original records and certified copies of original records of clinical findings, observations, laboratory reports, data sheets provided by the sponsor or other activities in the study, which are necessary for the reconstruction and evaluation of the study. The investigator will permit study-related monitoring, audit(s), IRB review(s) and regulatory inspection(s), with direct access to all the required source records.

All study records will be retained for a period of time as defined by the regulatory authority and per ICH E6 section 4.9 for the country in which the investigation is conducted. Generally, this means at least 2 years following the date on which the drug is approved by the regulatory authority for marketing for the purposes that were the subject of the investigation. In other situations (e.g., where the investigation is not in support of or as part of an application for a research or marketing permit), a period of 2 years following the date on which the entire clinical program is completed, terminated or discontinued or the investigational application under which the investigation is being conducted is terminated or withdrawn by the regulatory authorities.

In the event the Investigator retires, relocates or for any other reason withdraws from the responsibility for maintaining records for the period of time required, custody of the records may be transferred to any other person who will accept responsibility for the records. Notice of such a transfer must be given in writing to the Sponsor. The Investigator must contact the Sponsor prior to disposal of any records related to this study.

10.7 Reporting of Results

The Case Report Form (CRF) is an integral part of the study and subsequent reports. The CRF must be used to capture all study data recorded in the patient's medical record. The CRF must be kept current to reflect patient status during the course of the study. Only a patient screening and randomization number and patient initials will be used to identify the patient.

The monitor is responsible for performing on-site monitoring at regular intervals throughout the study to verify adherence to the protocol; verify adherence to local regulations on the conduct of clinical research; and ensure completeness, accuracy, and consistency of the data entered in the CRF.

CASI Pharmaceuticals, Inc. or a designated CRO will monitor completed Case Report Forms (CRFs). A case report form will be provided for each screened patient.

All protocol-required information collected during the study must be entered by the Investigator, or designated representative, in paper CRF or the Target e*CRF™, an Internet-based electronic data collection system, which is 21CFR Part 11 compliant.. All details of the CRF completion and correction will be explained to the investigator. The management module of Target e*CRF™, if used, includes edit check and query systems that seamlessly integrate with the data

entry system. All modifications to the data in the eCRF are tracked by an electronic audit trail (date and identity of the person making the change are instantaneously recorded). The actual date (and time, if applicable) of each assessment should always be entered in the CRFs. If the Investigator authorizes other persons to make entries in the CRF, the names, positions, and signatures of these persons must be indicated on the Site Delegation Log.

The Investigator, or designated representative, should complete the eCRF as soon as possible after information is collected, preferably on the same day that a study patient is seen for an examination, treatment, or any other study procedure. Any outstanding entries must be completed immediately after the final examination. By design, an explanation must be provided for all missing data, altered data, and/or out of range data.

The completed case report form must be reviewed and signed by the Investigator named in the study protocol or by a designated sub investigator after all the data was monitored and verified as final by the designated study monitor.

Final monitored and audited CRFs will be provided by the Sponsor to the sites at the end of the study in the format of a PDF file.

10.8 Confidentiality of Subject Data

The investigator will ensure that the confidentiality of the subjects' data will be preserved. In the CRF or any other documents submitted to the sponsor, the subjects will not be identified by their names, but by an identification system, which consists of their initials and number in the study. The investigator will maintain documents not meant for submission to the sponsor, e.g., the confidential subject identification code and the signed informed consent forms, in strict confidence.

11. REPORTING AND PUBLICATION

11.1 Confidentiality of Study Data

Any information relating to the study product or the study, including any data and results from the study, will be the exclusive property of the sponsor. The investigator and any other persons involved in the study will protect the confidentiality of this proprietary information belonging to SPONSOR.

11.2 Publication Policy

SPONSOR agrees to make the report of the multicenter study results available to investigators for preparing a publication of the results in meeting abstract or medical journal form. SPONSOR will have 30 days to review any proposed publication of the data for accuracy and proprietary information. The Study Chair has the first right of refusal of both first and last authorship position on manuscripts and meeting presentations.

13. APPENDIX A

National Cancer Institute Common Terminology Criteria for Adverse Events v. 4.03

http://evs.nci.nih.gov/ftp1/CTCAE/CTCAE_4.03_2010-06-14_QuickReference_5x7.pdf

14. APPENDIX B

ECOG Performance Status

Grade	ECOG
0	Fully active, able to carry on all pre-disease performance without restriction
1	Restricted in physically strenuous activity but ambulatory and able to carry out work of a light or sedentary nature, e.g., light house work, office work
2	Ambulatory and capable of all selfcare but unable to carry out any work activities. Up and about more than 50% of waking hours
3	Capable of only limited selfcare, confined to bed or chair more than 50% of waking hours
4	Completely disabled. Cannot carry on any selfcare. Totally confined to bed or chair
5	Dead

16. APPENDIX D

Appendix D. Selected Inhibitors and Inducers of CYP3A4

Inhibitors	Inducers
Protease inhibitors: ritonavir indinavir nelfinavir saquinavir	Anticonvulsants, mood stabilizers: phenytoin (anticonvulsant) carbamazepine oxcarbazepine
Macrolide antibiotics: erythromycin telithromycin clarithromycin	Barbiturates: Phenobarbital
Azole antifungals: fluconazole ketoconazole itraconazole	Non-nucleoside reverse transcriptase inhibitors: efavirenz nevirapine etravirine
Nefazodone (psychoactive and antidepressant)	Rifampicin & rifabutin (bactericidal)
Bergamottin (constituent of grapefruit juice)	Modafinil (stimulant)
Quercetin (nutritional supplement)	Hyperforin (constituent of St Johns Wort)
Aprepitant (antiemetic)	Cyproterone (antiandrogen, progestin)
Verapamil & diltiazem (calcium channel blocker)	Pioglitazone & troglitazone (antidiabetics)
Chloramphenicol (antibiotic)
